## 4 STATISTICAL ANALYSIS

This section provides information on definitions, derivations and analysis/data presentation per domain.

### 4.1 Study Population

The domain study population covers participant disposition, analysis sets, protocol deviations, demographics, baseline characteristics, medical history, prior and concomitant medication and study intervention compliance.

#### 4.1.1 Participant Disposition and Completion Status

##### 4.1.1.1 Definitions and Derivations

Participants are defined as entering the inpatient period if they received one or more doses of SZC.

##### 4.1.1.2 Presentation

Participant disposition will be listed and summarised by treatment group and overall. The number and percentages of participants in the following categories will be summarised for participants in the screened set:

- Participants enrolled;
- Participants entered inpatient period
- Participants randomised;
- Participants who were not randomised and associated reasons;
- Randomised participants who received treatment;
- Randomised participants who did not receive treatment and associated reasons;
- Randomised participants who completed treatment;
- Randomised participants who discontinued treatment and associated reasons
- Randomised participants who completed the study;
- Randomised participants withdrawn from the study and associated reasons;

The denominator used for percentages will be calculated as follows. The denominator for participants who are screened or who did not enter the inpatient period (and associated reasons) will be calculated using the number of screened participants. The denominator for participants who entered the inpatient period and received treatment, who entered the inpatient period and did not receive treatment (and associated reasons), randomised and not randomised (and associated reasons) will be calculated using the number of participants who entered the inpatient period. The remaining participant disposition categories will use the number of participants who were randomised for the denominator.

#### **4.1.2 Analysis Sets**

##### **4.1.2.1 Definitions and Derivations**

The definition for analysis sets is described in section 3.2.

##### **4.1.2.2 Presentation**

The number of participants in each of the analysis sets and the reasons for exclusion from each will be summarised for all screened participants by treatment group and overall.

#### **4.1.3 Protocol Deviations**

##### **4.1.3.1 Definitions and Derivations**

Important protocol deviations will be defined according to section 3.3.5, and determined in prior to database lock as outlined in the protocol management plan.

##### **4.1.3.2 Presentation**

All important protocol deviations will be listed and summarised by treatment group and overall for the FAS. Important protocol deviations will be further classified as either pandemic-related or excluding pandemic related important protocol deviations.

#### **4.1.4 Demographics**

##### **4.1.4.1 Definitions and Derivations**

The demographic and baseline characteristics include the following:

- Age (years);
- Age groups (18-64, 65-84 and 85 years and over);
- Sex (male, female);
- Race category (White, Black or African American, Asian, Native Hawaiian or Other Pacific Islander, American Indian or Alaskan Native, Other, Not reported);
- Ethnic group (Hispanic or Latino, Not Hispanic or Latino);
- Participant recruitment country;

#### **4.1.4.2 Presentation**

The demographic characteristics defined in Section 4.1.4.1 will be listed and summarised in total for the SSO and by treatment group and total for the SSR and FAS.

No formal tests of statistical significance will be performed on the demographic and baseline data.

#### **4.1.5 Baseline Characteristics**

##### **4.1.5.1 Definitions and Derivations**

Baseline body mass index (BMI; kg/m^2) will be calculated as baseline weight/baseline height where weight is in kg and height is in m.

##### **4.1.5.2 Presentation**

A separate table will summarize the participant baseline characteristics and will be listed and summarised in total for the SSO and by treatment group and total for the SSR and FAS. They will include:

- Baseline height (cm);
- Baseline weight (kg);
- BMI (kg/m^2);

#### **4.1.6 Disease Characteristics**

##### **4.1.6.1 Definitions and Derivations**

The following disease characteristics will be defined:

- Presence of heart failure (Yes/No, identified per Medical History using an SMQ of “Cardiac failure” with a narrow scope; SMQ Code: 20000004 which includes preferred terms of: Acute left ventricular failure, Acute pulmonary oedema, Acute right ventricular failure, Cardiac asthma, Cardiac failure, Cardiac failure acute, Cardiac failure chronic, Cardiac failure congestive, Cardiac failure high output, Cardiogenic shock, Cardiohepatic syndrome, Cardiopulmonary failure, Cardiorenal syndrome, Chronic left ventricular failure, Chronic right ventricular failure, Congestive hepatopathy, Cor pulmonale, Cor pulmonale acute, Cor pulmonale chronic, Ejection fraction decreased, Hepatojugular reflux, Left ventricular failure, Low cardiac output syndrome, Neonatal cardiac failure, Obstructive shock, Pulmonary oedema, Pulmonary oedema neonatal, Radiation associated cardiac failure, Right ventricular ejection fraction decreased, Right ventricular failure, Ventricular failure.

- Diabetes (Yes/No, identified per Medical History eCRF using an SMQ of “Hyperglycaemia/new onset diabetes mellitus” with a narrow scope; SMQ Code: 20000041 which includes preferred terms of: Acquired generalised lipodystrophy, Blood 1,5-anhydroglucitol decreased, Blood glucose increased, Diabetes complicating pregnancy, Diabetes mellitus, Diabetes mellitus inadequate control, Diabetes with hyperosmolarity, Diabetic arteritis, Diabetic coma, Diabetic coronary microangiopathy, Diabetic hepatopathy, Diabetic hyperglycaemic coma, Diabetic hyperosmolar coma, Diabetic ketoacidosis, Diabetic ketoacidotic hyperglycaemic coma, Diabetic ketosis, Diabetic metabolic decompensation, Diabetic wound, Euglycaemic diabetic ketoacidosis, Fructosamine increased, Fulminant type 1 diabetes mellitus, Gestational diabetes, Glucose tolerance impaired, Glucose tolerance impaired in pregnancy, Glucose urine present, Glycated albumin increased, Glycated serum protein increased, Glycosuria, Glycosuria during pregnancy, Glycosylated haemoglobin abnormal, Glycosylated haemoglobin increased, Hepatogenous diabetes, Hyperglycaemia, Hyperglycaemic crisis, Hyperglycaemic hyperosmolar nonketotic syndrome, Hyperglycaemic seizure, Hyperglycaemic unconsciousness, Impaired fasting glucose, Insulin resistance, Insulin resistant diabetes, Insulin-requiring type 2 diabetes mellitus, Ketoacidosis, Ketonuria, Ketosis, Ketosis-prone diabetes mellitus, Latent autoimmune diabetes in adults, Maternally inherited diabetes and deafness, Monogenic diabetes, Neonatal diabetes mellitus, Neonatal hyperglycaemia, New onset diabetes after transplantation, Pancreatogenous diabetes, Pseudodiabetes, Steroid diabetes, Type 1 diabetes mellitus, Type 2 diabetes mellitus, Type 3 diabetes mellitus, Urine ketone body present)
- Renin-angiotensin-aldosterone system inhibitors (RAASi) use at screening (Yes/No, identified per Concomitant Medication eCRF as CMCLASCD in ('C09AA', 'C09BA', 'C09BB', 'C09BX', 'C09CA', 'C09DA', 'C09DB', 'C09DX', 'C09XA') where Start Date is prior to admission date for in-patient phase of hospital visit)
- CKD diagnosis (identified per Medical History eCRF using a LLT containing “Chronic kidney disease”)
- CKD stage (derived based on eGFR value), calculated as:
  - Grade 1 ( $eGFR \geq 90$ )
  - Grade 2 ( $60 \leq eGFR < 90$ )
  - Grade 3a ( $45 \leq eGFR \leq 59$ )
  - Grade 3b ( $30 \leq eGFR \leq 44$ )

- Grade 4 ( $15 \leq \text{eGFR} \leq 29$ )
- Grade 5 ( $\text{eGFR} < 15$ )
- Baseline  $\text{K}^+$  ( $5.0 < \text{K}^+ \leq 5.5$  versus  $5.5 < \text{K}^+ \leq 6.5$  mmol/L)
- Duration of index hospitalisation ( $<7$  days versus  $\geq 7$  days)

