Analyses will be further detailed in the statistical analysis plan which will be finalised within 90 days of first participant enrolled. It should be noted that death without prior hospitalisation or ED visits is seen as negligible. As such, the way death is treated (as outcome or censoring) will not dramatically affect the outcomes.

Primary Endpoint

Occurrence (yes/no) of NK (K⁺ between 3.5 and 5.0 mmol/L, inclusive) at 180 days post-discharge will be analysed using a logistic regression model with response as the dependent variable and randomised treatment group as the independent variable. Participants who discontinue treatment with a K⁺ measurement at 180 days post-discharge will have this value used irrespective of treatment discontinuation. Use of rescue therapy for HK will be considered to be non-response. Down-titration (including discontinuation) of RAASI (ie, angiotensin-converting enzyme inhibitors, angiotensin receptor blockers, and mineralocorticoid receptor antagonists) will be considered to be non-response. Participants who die of any cause prior to 180 days post-discharge or who are lost to follow-up for any reason will be considered to be non-response. Sensitivity analyses will evaluate the impact of considering this as non-response versus only evaluating completers will be assessed.

Secondary Efficacy Endpoints

1. *Time to first occurrence of any component of all-cause hospital admission, or ED visit with HK as a contributing factor, or all-cause death, or use of rescue therapy for HK at any time post-discharge up to 180 days* will be analysed using a log-rank test. In addition, a Cox proportional hazards model will be used for estimation with randomised treatment group as the independent variable. Participants who discontinue treatment will continue to be followed up to the first component of the composite endpoint. Rescue therapy for HK will be considered an event. Participants who require hospital admission or ED visits without HK as a contributing factor will continue to be followed up to the first component of the composite endpoint. Participants who die of any cause will be considered an event. Participants who are lost to follow-up will be censored at the date of loss to follow-up. Participants who have RAASI down-titration (including discontinuation) will continue to be followed up to the first component of the composite endpoint.

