- ^k Treatment with sodium zirconium cyclosilicate (SZC) will be established while the participant is in the hospital. Only participants randomised to SZC will be dispensed study intervention during the outpatient phase. Any time study drug dose is adjusted, or if in either treatment arm a concomitant medication which may affect K⁺ levels is changed (eg, use of renin angiotensin-aldosterone system inhibitors [angiotensin-converting enzyme inhibitors, angiotensin receptor blocker, mineralocorticoid receptor antagonists] or diuretics), the participant needs to return to the site 7 (± 2) days later for a K⁺ measurement and recording of adverse events and concomitant medications. During the inpatient phase, drug dispensation will occur every day.
- ^l Central laboratory K⁺ results at baseline are not necessary to initiate the study intervention as long as all eligibility criteria are met (only local assessment of K⁺ within 24 hours of treatment initiation is required).
- ^m If dose titration occurs at any time during the outpatient phase, unscheduled dispensation visits will be performed.
- ⁿ Relative to the date of randomisation (Visit 3)
- ^o Relative to the date of Visit 10/EOT.

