### **4.1.8 Prior and Concomitant Medications**

#### **4.1.8.1 Definitions and Derivations**

Medications received prior to or concomitantly with study treatment will be coded using the WHO Drug Dictionary [Version March 2021 (or a later version if updated during the study)], Anatomical Therapeutic Chemical (ATC) Classification codes.

Prior medications and concomitant medications are defined as follows:

Prior medications are those taken with a stop date prior to the first dose date of study treatment during the inpatient period.

Concomitant medications during the inpatient period are those with a stop date prior to the first dose of study treatment during the outpatient period and either a start date on or after the first dose date of study treatment during the inpatient period, or those with a start date before, and either a stop date on or after the first dose date of study treatment during the inpatient period or those which are ongoing.

Concomitant medications during the outpatient period are those with a start date on or after the first dose date of study treatment during the outpatient period, or those with a start date before, and either a stop date on or after the first dose date of study treatment during the outpatient period or those which are ongoing.

If a medication cannot be classified as “prior” or “concomitant during the inpatient period” or “concomitant during the outpatient period” after applying imputation rules for missing/incomplete dates, it will be classified as concomitant during the outpatient period.

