#### 4.2.25.2 Derivations

RAASI use at discharge is derived using the concomitant medication rescue medications eCRF as where one or more CMCLASCD in ('C09AA', 'C09BA', 'C09BB', 'C09BX', 'C09CA', 'C09DA', 'C09DB', 'C09DX', 'C09XA') where Start Date is prior to the date of randomisation and End Date is ongoing or after the date of randomisation. RAASI use at day 90 post-discharge is derived using the concomitant medication rescue medications eCRF as above where Start Date is prior to day 90 post-discharge and End Date is ongoing or after day 90 post-discharge. RAASI use at day 180 post-discharge is derived using the concomitant medication rescue medications eCRF as above where Start Date is prior to day 180 post-discharge and End Date is ongoing or after day 180 post-discharge. A RAASI dose increase at 90 and 180 days post-discharge is defined where the CMDECOD at discharge is different at 90 or 180 days or where CMDECOD at 90 or 180 matches that at discharge but the CMDOSTXT is greater than at discharge. A RAASI dose decrease at 90 and 180 days post-discharge is defined, where CMDECOD at 90 or 180 days matches that at discharge but the CMDOSTXT is less than at discharge.

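### The SAP's RAASi-use code list holds only C09 codes, so participants whose only RAASi is an MRA are labelled non-users if, as assumed here, single-agent MRAs are coded outside C09

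*SAP*

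**What the plan says.** **Protocol.** The Synopsis, in its text on the primary endpoint, spells out RAASi as a closed list: "angiotensin-converting enzyme inhibitors, angiotensin receptor blockers, and mineralocorticoid receptor antagonists". Footnote k to the Schedule of Activities (section 1.3) names the same three classes and sets diuretics apart from them: "use of renin angiotensin-aldosterone system inhibitors [angiotensin-converting enzyme inhibitors, angiotensin receptor blocker, mineralocorticoid receptor antagonists] or diuretics".

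**SAP.** Section 4.1.6.1 defines "Renin-angiotensin-aldosterone system inhibitors (RAASi) use at screening" as Yes or No, from "CMCLASCD in ('C09AA', 'C09BA', 'C09BB', 'C09BX', 'C09CA', 'C09DA', 'C09DB', 'C09DX', 'C09XA" plus a start-date condition. The same codes recur in the subgroup sections for the primary endpoint and all six secondary endpoints (4.2.2.6, 4.2.3.7, 4.2.4.7, 4.2.5.7, 4.2.6.7, 4.2.7.7, 4.2.8.7). They recur again in 4.2.25.2 for exploratory endpoint #17, where "RAASI use at discharge is derived using the concomitant medication rescue medications eCRF", with parallel rules for days 90 and 180. The codes belong to the ATC system, as section 4.1.8.1 makes clear: "Medications received prior to or concomitantly with study treatment will be coded using the WHO Drug Dictionary".

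**Down-titration events.** Protocol section 4.2 and Appendix A 5 give the adjudication committee the task of identifying RAASi down-titration and discontinuation from the reported concomitant medications. The C09 list is not mentioned there, nor in the SAP derivation of that endpoint (4.2.6.2).

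**The concern.** A derived variable should pick out the drug classes that the protocol puts under its name. Here the protocol names three classes, and the SAP's rule draws on one ATC group. If the third class is coded elsewhere, the RAASi-use flag measures something narrower than the protocol's RAASi, and nobody has said so.

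Two things are at stake. First, the flag is a covariate and a subgroup factor, so true users placed among the non-users blur both. Second, exploratory endpoint #17 addresses the ability to continue RAASi. Protocol section 2.2 presents the withdrawal of these drugs to manage hyperkalaemia as a central clinical problem. A rule blind to one class would overstate continuation for anyone who gives up that class and keeps another.

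**Working it through.** No alpha, power or sample-size figure is involved. The check compares the two definitions and then traces where the SAP's rule is used.

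**1. Compare the definitions.** Protocol: ACE inhibitors, ARBs, MRAs. SAP: C09AA, C09BA, C09BB, C09BX, C09CA, C09DA, C09DB, C09DX, C09XA. All nine codes begin with C09; none lies outside it.

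**2. Look for another rule that brings MRAs in.** No drug-name rule, eCRF flag or further code does so. SAP section 2 declares two changes to the protocol's analyses (the Per Protocol Set and the ECG data from one site). Neither these nor the SAP amendment history narrows RAASi.

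**3. State the outside premise.** The documents do not say where ATC places MRAs. Assumption: single-agent MRAs are coded in C03 (C03DA). If so, the list covers two of the protocol's three classes. If the sponsor's dictionary instead placed them under a listed code, the list would be complete and the point would fall.

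**4. Apply the rule, under that assumption, to each kind of participant** (date conditions met).

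| Drugs taken | RAASi user by protocol | SAP flag | Exploratory #17 |
|---|---|---|---|
| ACE inhibitor or ARB only | Yes | Yes | Seen |
| ACE inhibitor or ARB, plus MRA | Yes | Yes | MRA start, stop or dose change not seen; stopping the MRA leaves the participant counted as still on RAASi |
| MRA only | Yes | **No** | Not counted as on RAASi at discharge, day 90 or day 180 |
| None of these | No | No | Correctly absent |

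I read the dose-change rules in 4.2.25.2 as applying to the records that the list selects.

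**5. Trace the use of the flag.**
- *Uses it:* the multivariable logistic sensitivity model (4.2.2.5); the multivariable Cox model and the weighting model for loss to follow-up (4.2.3.5), with the endpoints that refer to that section; the multivariable negative binomial models (4.2.5.5, also applied in 4.2.8.5, and 4.2.14.5); the potassium sensitivity model (4.2.13.5); the additional Cox models (4.2.18.5, 4.2.20.5, 4.2.21.5, 4.2.23.5, 4.2.24.5); the RAASi subgroups; and the disease-characteristics table (4.1.6.2).
- *Does not use it:* the primary logistic model, with treatment and country (4.2.2.4); the log-rank test by treatment and the Cox model with treatment and country (4.2.3.4); the count models, with treatment and a time offset (4.2.5.4); and the adjudicated down-titration events, both as non-response and as an endpoint (4.2.6.2).

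**6. Size.** Misclassified at baseline = N × p, where N is the number randomised and p is the share whose only RAASi is an MRA. N is about 130 (Protocol section 4.1). The documents give no p and no overall RAASi prevalence. Only a conversion is possible: 130 × 0.01 = 1.3 participants for each percentage point of p.

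**The case against.** The strongest reply is that little of consequence depends on the list, and most of that reply stands.

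- **The ATC placement is not in the documents.** True. The point is conditional on it. But the SAP's codes can be read only through that system, and the sponsor can settle the matter in its own dictionary.
- **A reader might infer that every MRA user is classed as a non-user.** That is not supported. One listed code is enough for Yes, so an MRA user who also takes a C09 drug is flagged correctly at baseline.
- **A reader might infer that the primary endpoint, or time to RAASi down-titration, is miscounted.** The documents do not support this. Those events are adjudicated, and no primary analysis in the testing hierarchy contains the flag.
- **A reader might infer that RAASi use sits in every adjusted model.** It does not. The country-adjusted logistic and Cox models and the eGFR model (4.2.22.4) have no RAASi term. The multivariable models for the primary and the time-to-event secondary endpoints also run only if event-count conditions are met, as do the subgroups.
- **An MRA-only participant could have an adjudicated down-titration while sitting in the non-user subgroup of that endpoint (4.2.6.7).** This can happen under the protocol's definition, but it carries limited weight. Anyone who starts a RAASi after the date cut-off (admission in 4.1.6.1, informed consent in the subgroup sections) is also labelled No and can later have an event. Adding codes would not remove that pattern. It also depends on the adjudication charter's definition, which is not available here.
- **Exploratory #17 is descriptive, with no test.** True, but a descriptive count of who stayed on RAASi should still count what the protocol calls RAASi.

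These replies narrow the point without removing it. None explains why the SAP's list should be narrower than the protocol's definition.

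**Conclusion.** The point holds as a mismatch between the protocol's definition and the SAP's stated rule, conditional on one premise: that single-agent MRAs are coded outside C09 in the WHO Drug version used. Under that premise the baseline flag is wrong for participants whose only RAASi is an MRA, and exploratory #17 misses MRA changes even in participants flagged Yes.

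The consequences are confined to supporting models, subgroups, one baseline table and one descriptive endpoint. No confirmatory result changes. A reader might want a head count, but any such figure would need inputs that the documents do not contain, so none is given. Since the SAP declares no narrower definition, an oversight is more likely than a deliberate choice.

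**What to change.** Confirm the ATC placement of MRAs in the dictionary version used. Then add the MRA class code or codes in all nine sections that carry the list: 4.1.6.1, the seven subgroup sections (1 + 7 + 1 = 9 in all) and 4.2.25.2. It would be safer to define the list once in 4.1.6.1 and refer to it elsewhere. Check the result against the RAASi definition in the adjudication charter, so that the flag and the adjudicated events describe the same drugs. If a narrower definition is intended, declare and justify it in SAP section 2 and label the variable accordingly.

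The cost is a text edit in nine places and a change to the derivation program. No new data are needed: Protocol section 6.7 already requires all medication to be recorded, and SAP 4.1.8.1 already codes it by ATC. The change should be made before database lock.

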4 STUDY DESIGN

4.1 Overall Design

- This is a Phase 4, randomised, controlled, open-label, parallel-group, multicentre study in participants with CKD treated for HK whilst in hospital.
- Participants from 30 to 50 sites in 4 to 7 countries will be screened for enrolment. Assuming a 20% drop out rate from enrolment to randomisation and a 20% drop out post-discharge (post-randomisation), approximately 163 participants will have to be enrolled to achieve 104 evaluable participants (52 per arm). In total, up to a maximum of 163 participants will be enrolled, resulting in approximately 130 participants discharged and randomised and 104 evaluable participants (52 per arm).
- The study plans to enrol approximately equal numbers of participants with mild HK (K^+ between > 5.0 and ≤ 5.5 mmol/L) and with moderate/severe HK (K^+ between > 5.5 and ≤ 6.5 mmol/L), with a minimum of 30% of the enrolled participants in either group.
- During the in-hospital phase, participants will be treated with SZC as per local label (correction and/or maintenance treatment, see Section 6.1), starting at baseline and based on local K^+ measurement obtained within 24 hours of treatment initiation:
 - Participants with HK (K^+ between > 5.0 and ≤ 6.5 mmol/L): 1) stop current K-binder if any, 2) start SZC correction dose (note: participants currently on SZC should continue SZC correction dose, up to 72 hours).
 - Participants currently receiving any treatment for the current episode of HK and are already NK at baseline ($K^+ \leq 5.0$ mmol/L): 1) stop any current K-binder, 2) start SZC maintenance dose (note: participants currently on SZC maintenance dose should continue SZC maintenance dose).
 - All treatment decisions, including modification of the ongoing therapy for HK, must be based on the investigator's medical judgement of the participant's best interest.
- At discharge, NK participants who have been treated with SZC for between 1 and 21 days whilst in hospital and are started on SZC maintenance dose will be randomised in a 1:1 ratio to one of the following arms:
 - Arm A: Participants discharged with SZC, as per local label, to manage HK until the end of the outpatient phase
 - Arm B: Participants discharged with SoC, as per local practice, to manage HK until the end of study.

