5.1 Inclusion Criteria

Participants are eligible to be included in the study only if all of the following criteria apply:

Age

- 1 Must be 18 years of age or older, at the time of signing the informed consent

Type of Participant and Disease Characteristics

- 2 Admitted to hospital (inpatient care; directly or from ED)
- 3 With:
 - Diagnosed CKD (any stage)
 - or
 - eGFR $< 90 \text{ mL/min/1.73 m}^2$ at, or within 3 months of, study screening, based on the Chronic Kidney Disease Epidemiology Collaboration (CKD-EPI) equation ([Levey et al, 2009](#)). Note: Race/ethnicity should not be included in CKD-EPI equation calculation.
- 4 Local laboratory K^+ measurement within 24 hours of baseline visit (visit 2), where result is either:
 - Hyperkalaemic as defined by site's local practice and $\text{K}^+ \leq 6.5 \text{ mmol/L}$
 - Or, normokalaemic: K^+ between ≥ 3.5 and $\leq 5.0 \text{ mmol/L}$, where patient started and is receiving treatment for this episode of HK.

Sex

- 5 Male or female

Informed Consent

- 6 Capable and willing of giving signed informed consent as described in [Appendix A](#) which includes compliance with the requirements and restrictions listed in the informed consent form (ICF) and in this protocol.

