### **4.1.7 Medical History and Concomitant Disease**

#### **4.1.7.1 Definitions and Derivations**

Medical history will be coded using the Medical Dictionary for Regulatory Activities (MedDRA) [Version 24.1 (or a later version if updated during the study)].

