#### 4.2.2.6 Subgroup Analyses

Subgroup analyses will be performed using separate logistic regression models, as per section 4.2.2.4, by age (18-64, 65-84 and  $\geq 85$  years), sex (female, male), recruitment country (France, Italy, Spain, UK, Belgium and Netherlands), presence of heart failure (Yes/No, identified per Medical History using an SMQ of “Cardiac Failure”; SMQ Code: 20000004), diabetes (Yes/No, identified per Medical History eCRF using a PT of “Type 2 diabetes mellitus”), RAASI use at screening (Yes/No, identified per Concomitant Medication eCRF as CMCLASCD in (‘C09AA’, ‘C09BA’, ‘C09BB’, ‘C09BX’, ‘C09CA’, ‘C09DA’, ‘C09DB’, ‘C09DX’, ‘C09XA’) where Start Date is prior to date of informed consent), CKD stage, without diagnosis of CKD (but eGFR  $< 90$  ml/min/1.73m^2), baseline  $K^+$  ( $5.0 < K^+ \leq 5.5$  versus  $5.5 < K^+ \leq 6.5$  mmol/L) at baseline, an alternative baseline  $K^+$  categorisation ( $5.0 < K^+ \leq 5.5$ ,  $5.5 < K^+ \leq 6.0$ , and  $6.0 < K^+ \leq 6.5$  mmol/L) and by duration of index hospitalisation ( $< 7$  days versus  $\geq 7$  days). Subgroup analyses will only be conducted providing there are 10 or more events per subgroup category.

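### CKD diagnosis rests on a single text match in the coded lowest level term, so diagnosed participants coded to a synonym could be analysed in the subgroup without a CKD diagnosis

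*SAP*

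**What the plan says.** Inclusion criterion 3 (Protocol 5.1) has two routes. One is "Diagnosed CKD (any stage"); the other is an eGFR below 90. It ties no particular term or coding rule to the diagnosis.

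SAP 4.1.7.1 states: "Medical history will be coded using the Medical Dictionary for Regulatory Activities (MedDRA"), version 24.1 or later. SAP 4.1.6.1 then derives the diagnosis flag. It is "identified per Medical History eCRF using a LLT containing" the text *Chronic kidney disease*. The SAP adds no synonym list, preferred-term rule, standardised query, eligibility field or medical review.

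In the same section heart failure is "identified per Medical History using an SMQ of" cardiac failure, narrow scope, with its preferred terms listed. Diabetes is handled there in the same way. CKD stage is a separate variable: "CKD stage (derived based on eGFR value), calculated as" six eGFR bands.

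The subgroup "without diagnosis of CKD (but eGFR" below 90) appears in SAP 4.2.2.6 for the primary endpoint and in 4.2.3.7, 4.2.4.7, 4.2.5.7, 4.2.6.7, 4.2.7.7 and 4.2.8.7 for the six secondary endpoints. None of these sections derives the diagnosis or refers back to 4.1.6.1 for it. All carry the same condition: "Subgroup analyses will only be conducted providing there are 10 or more events per subgroup category".

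**The concern.** A text match on a lowest level term is sensitive to how a history was coded. Two participants with the same disease can fall on opposite sides of the flag if one record is coded to a term containing the phrase and the other to, say, a chronic renal failure term. Recruitment spans six countries, according to the subgroup list, so varied recording is foreseeable.

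This kind of error runs one way. It moves diagnosed people into a group meant to exclude them, and if that group is small, a modest miss rate can make up much of it. The subgroup addresses whether participants admitted on eGFR alone respond like those with established CKD. If many of its members do have a diagnosis, that question is not answered. The disease-characteristics table (SAP 4.1.6.2) would also report too few participants with diagnosed CKD, in a trial whose population is defined by that disease.

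**Working it through.** **Tracing the rule.** The plan states no figure on this point, so the first check is of the text.

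1. The only derivation of CKD diagnosis in either document is the LLT match in SAP 4.1.6.1.
2. The seven subgroup sections need a diagnosis flag and supply none. Applying 4.1.6.1 to them is an inference, but there is no competing definition.
3. Take a participant with diagnosed CKD coded to an LLT without the phrase. The flag is negative. With eGFR below 90 the participant enters the subgroup. With eGFR of 90 or above the participant does not, but is still missed in the table.
4. Step 3 requires that such synonym terms exist as separate LLTs. The documents do not reproduce the dictionary, so this is an assumption to confirm.

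**Illustrative size.** The documents give no coding split, so both rates below are assumed.

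- N = 130, from Protocol 4.1 ("resulting in approximately 130 participants discharged and randomised").
- u = share truly without a diagnosis, 10–30% (assumed).
- m = share of diagnosed CKD missed by the match, 5–30% (assumed).
- All those missed have eGFR below 90 (assumed; a lower share reduces every figure).

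Truly undiagnosed = N × u. Wrongly added = N × (1 − u) × m. Share wrong = added / (undiagnosed + added).

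| u (undiagnosed) | m = 5% | m = 10% | m = 20% | m = 30% |
|---|---|---|---|---|
| 10% (13) | 5.85 added, 31% | 11.7, 47% | 23.4, 64% | 35.1, 73% |
| 20% (26) | 5.2, 17% | 10.4, 29% | 20.8, 44% | 31.2, 55% |
| 30% (39) | 4.55, 10% | 9.1, 19% | 18.2, 32% | 27.3, 41% |

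The extremes are 4.55 / (39 + 4.55) = 10% and 35.1 / (13 + 35.1) = 73%.

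**Effect on the 10-event threshold.** Protocol 9.2.2 assumes main secondary event proportions of 17% and 43.2%. With equal arms the pooled rate is (17 + 43.2) / 2 = 30.1%. If the subgroup shares that rate, 10 expected events need 10 / 0.301 = 33 participants. With u = 10%, a correct flag gives 13 × 0.301 = 3.9 events. With m = 20%, the labelled subgroup has 13 + 23.4 = 36.4 participants and 36.4 × 0.301 = 11.0 expected events. An analysis expected not to run would then be expected to run, with 64% of its participants wrongly placed.

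**The case against.** The strongest reply is that the mechanism depends on dictionary content and coded histories that the documents do not show. That stands, and it is why the point is conditional. A reader might infer that only histories the site worded as chronic kidney disease are captured. The text does not support this: the match is on a coded term, and any longer term containing the phrase also qualifies.

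A reader might also infer that CKD alone is treated more narrowly than the other conditions. That holds within 4.1.6.1. It does not carry over to diabetes in 4.2.2.6 and 4.2.3.7, which use a single preferred term instead of the standardised query. These sections restate some definitions differently from 4.1.6.1, so the missing CKD derivation may be only a missing cross-reference. Adding one would still lead to the same text match.

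The consequence is limited. Subgroups are outside the testing hierarchy in SAP 3.3.4, and this one is not among those named in Protocol 9.4.3.2, though that section allows additions. If only 13 participants were truly undiagnosed, a perfect flag would probably leave too few main secondary events to run the analysis. That is fair, but not running it would then be the correct outcome, whereas mislabelling could cause it to run. Finally, SAP 4.1.7.2 tabulates medical history by preferred term, so kidney histories under other preferred terms will be visible. That table does not correct the flag.

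**Conclusion.** The point holds in conditional form. As written, the plan would place a diagnosed participant with eGFR below 90 in the undiagnosed subgroup if the history is coded to an LLT without the phrase, and would undercount diagnosed CKD in the disease-characteristics table. The real size is unknown. The 10–73% range rests on the assumed rates above and on every missed participant having eGFR below 90.

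Two stronger readings are not supported. The first is that most of the subgroup will be misclassified. That needs a small undiagnosed share together with a substantial miss rate, and the documents supply neither. The second is that the trial's main results are at risk. The primary and secondary tests do not use the flag, the adjusted models use CKD stage from eGFR, and sample size and type I error are untouched. The damage is confined to seven subgroup analyses and one descriptive table.

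**What to change.** Replace the text match in SAP 4.1.6.1 with one of the following: a preferred-term definition; a medically reviewed term list fixed before database lock; or the inclusion criterion 3 eligibility record, if the route of entry was captured. Medical review should decide whether any nephropathy term counts as diagnosed CKD. Counting all of them automatically could create the opposite error, since criterion 3 asks for diagnosed CKD and does not equate the two.

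Cite that single flag in 4.1.6.1 and in all seven subgroup sections. As part of the review, confirm in the MedDRA version used which CKD synonyms are LLTs without the phrase, and count the participants affected.

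The cost is one definition change and a one-off term review. No new data are needed.
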